1. INTRODUCTION

1.1 Literature Review

Over the last years a significant improvement in the treatment of patients with colon cancer has been reported. This has been attributed to the improvement of the staging techniques, as well as the optimization of the surgical management. However, the current five-year survival rates of colon cancer patients in European countries ranges from 32% to 64%. [1]. This variation could be due to treatment discrepancies and the lack of adherence to the international guidelines [2].

Surgical treatment of colon cancer includes the radical resection of the tumour (colectomy). Following resection, the specimen is histopathologically examined, the disease is staged and further treatment is determined. Neoadjuvant treatment (radiotherapy or/and chemotherapy) for colon cancer has not been yet approved, unlike rectal cancer, where neoadjuvant treatment is recommended for specific disease stages [3].

Preoperative staging of colon cancer aims to identify those patients with remote metastatic disease, who will, more likely, not benefit from upward surgery. Recent developments in colon cancer management, demanding more precise local disease staging, to identify those patients who will likely benefit from neoadjuvant chemotherapy, are still at a clinical trial stage [4].

Preoperative treatment depends on the disease stage, which is defined by the tumour's invasion in the colonic wall, the dissemination in nearby organs or lymph nodes, and the presence of distal metastases. The stage is first evaluated radiologically and then confirmed via histopathological examination of the specimen. Imaging is an already approved tool for the staging of colonic cancer, while in some studies the combination of different imaging methods has been reported to improve the initial evaluation [5, 6, 7, 8, 9, 10].

Over the last years, evaluation of the circumferential resection margin (CRM) is also recommended in the preoperative staging of patients with colon cancer. This assessment is particularly important for tumours located at the cecum, right, or left colon, since these areas lack of mobile mesocolon and therefore it is possible to infiltrate the retroperitoneal resection margin.

Nevertheless, the retroperitoneal invasion of these tumours has not been evaluated adequately as a preoperative marker for both local recurrence and for the selection of patients who may benefit from neoadjuvant treatment. In various studies the percentage of retroperitoneal resection margin's infiltration was between 7-10% for cecum and right colon adenocarcinomas, while its presence was identified as a risk factor for local recurrence. The retroperitoneal surface infiltration was preoperatively evaluated with the combination of imaging methods and the findings were postoperatively compared with the histopathological features of the specimen [11, 12].

A more precise, imaging based, preoperative staging, could lead to a more targeted neoadjuvant treatment for patients with advanced disease, with the introduction of chemo- and/or radiotherapy. This approach could result to the downstaging of the tumour, with better short and long term oncological results.

2. OBJECTIVE

2.1 Description of the proposed project

The objective of this study is the evaluation of different imaging methods for the optimal preoperative staging of colon cancer patients. Imaging findings will be compared with the histopathologic results of the specimen following surgical resection.

3. MATERIAL AND METHODS

3.1 Population

The sample will consist of males and females aged 18 to 90 years.

3.2 Diseases

The study will include patients with colon cancer that will meet the current criteria surgical resection based on the principles of complete mesocolic excision (CME).

3.3 Inclusion / Exclusion Criteria

Inclusion criteria are the following:

- Histologically confirmed colonic adenocarcinoma
- Patient 18 to 90 years old
- Abscence of comorbidities that may affect treatment
- Signed informed consent of the patient

Exclusion criteria are the following:

- Inability to receive or contraindication for intravenous contrast
- Renal impairment
- Previous allergies to intravenous contrasts
- Incompatible implants with magnetic resonance imaging
- Claustrophobia
- Active sepsis or systemic infection
- Untreated physical and mental disability
- Lack of compliance with the protocol process
- Non-granting of signed informed consent

3.4 Study Arms

In this study there will be one arm. All prospectively included patients with colon cancer will be preoperatively submitted to MRI for staging. The evaluation of the diagnostic accuracy will be based on the cross-examination with the CT scan and the pathology results.

The MRI protocol will include the following imaging series: T1 and T2 in axial and coronal plane before the administration of intravenous contrast, diffuse weight imaging in axial plane and T1 after the administration of intravenous contrast.

The CT scan protocol will include the following: per os and intravenous administration of contrast, axial slices of 0.3mm thickness and reconstruction per 1mm, multi-planar reformation and three-dimensional volume rendering.

3.5 Anesthesia

Patients will receive general anesthesia.

3.7 Primary endpoint

Diagnostic accuracy in T stage. Evaluation of diagnostic accuracy in the T stage assessment
[Time Frame: 1 month postoperatively]

3.8 Secondary endpoints

Secondary endpoints of the present study are:

Diagnostic accuracy in N stage. Evaluation of diagnostic accuracy in the presence of local or distant metastatic lymph nodes

[Time Frame: 1 month postoperatively]

Diagnostic accuracy in the retroperitoneal resection margin. Evaluation of diagnostic accuracy in the retroperitoneal resection margin

[Time Frame: 1 month postoperatively]

Diagnostic accuracy in peritoneal or nearby organ infiltration. Evaluation of diagnostic accuracy in the peritoneal or nearby organ infiltration

[Time Frame: 1 month postoperatively]

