3.9 Calculation of the sample size

The sample size calculation was based on the primary endpoint. According to the literature, the specificity of MRI of the T1/T2 vs T3/T4 differentiation is 84%. Therefore, for a prospective study with alpha: 5%, power: 80%, d=10% and dropout rate: 30%, the estimated number of patients is 120.

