3.11 Blindness

There will be no blindness at the level of the patient, the treating physicians (surgeon, oncologist, radiotherapist) and the researcher who will record the data.

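### Imaging accuracy for the retroperitoneal margin is judged against a margin cut by a surgeon who is not blinded to the imaging, so a correct MRI warning that leads to a clear margin counts as a false positive

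*Protocol*

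**What the plan says.** The endpoint in section 3.8 is "Evaluation of diagnostic accuracy in the retroperitoneal resection margin". That section names no reference standard and does not define a positive imaging call.

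The reference has to be taken from elsewhere. Section 2.1 states: "Imaging findings will be compared with the histopathologic results of the specimen following surgical resection". Section 3.4 adds CT: "The evaluation of the diagnostic accuracy will be based on the cross-examination with the CT scan and the pathology results".

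On timing, section 3.4 says: "All prospectively included patients with colon cancer will be preoperatively submitted to MRI for staging". On masking, section 3.11 says: "There will be no blindness at the level of the patient, the treating physicians (surgeon, oncologist, radiotherapist"; it makes no exception for MRI or CT. Section 3.2 describes the operation as "surgical resection based on the principles of complete mesocolic excision (CME".

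No section says whether the retroperitoneal plane may follow the imaging, whether a change of plane is recorded, or how such a case is scored. Section 1.1 discusses retroperitoneal invasion as a possible preoperative marker. It describes earlier work in which infiltration of the retroperitoneal surface was assessed on imaging and then compared with the specimen. On frequency it reports that "the percentage of retroperitoneal resection margin's infiltration was between 7-10% for cecum and right colon adenocarcinomas".

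**The concern.** T stage describes the tumour and depends little on where the surgeon cuts. A resection margin is different, because the dissection helps to create it. When the surgeon knows the imaging, the test under evaluation can change the standard it is judged by.

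Suppose MRI correctly shows tumour at the retroperitoneal surface, the plane is widened and the pathologist reports a clear margin. The MRI call was right about the tumour, yet the two-by-two table records a false positive. Conversely, suppose MRI misses the involvement, but CT or the operative findings lead to a wider plane. The margin is again clear, and the miss becomes a true negative.

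At stake is the reading of one secondary endpoint. The estimates would mix how well MRI sees retroperitoneal invasion with how the surgeon responded to what was seen. An analysis plan could not separate the two afterwards unless the change of plane was recorded at the time of surgery.

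**Working it through.** **The plan's own figure.** Section 3.9 gives N = 120 from a proportion of 84%, d = 10%, alpha 5%, power 80% and 30% dropout. With one-sided alpha, n = (1.645 + 0.842)² × 0.84 × 0.16 / 0.10² = 83.1, rounded up to 84, and 84 / 0.70 = 120. The figure reproduces and is not in dispute. It serves only to give 84 evaluable patients.

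**Inputs to the illustration**
- Evaluable patients: 120 × 0.70 = 84 (section 3.9).
- True retroperitoneal involvement: 10%. This is an assumption, set at the upper end of the 7-10% in section 1.1. That range is a margin-infiltration rate, and so is observed after surgery, and it is for cecum and right colon only.
- True sensitivity 80% and specificity 90%: assumptions. The protocol gives neither for this endpoint.
- c = fraction of correctly flagged margins that are cleared; m = fraction of MRI misses that are cleared. The documents give neither.

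**True table.** Involved: 84 × 0.10 = 8.4. True positives TP = 0.8 × 8.4 = 6.72; misses FN = 1.68. Not involved: 75.6. TN = 0.9 × 75.6 = 68.04; FP = 7.56. True PPV = 6.72 / (6.72 + 7.56) = 47%.

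**Observed table when margins are cleared.** A number c·TP moves to false positive, and m·FN moves to true negative:
- Sensitivity = (1−c)TP / [(1−c)TP + (1−m)FN]
- Specificity = (TN + m·FN) / (TN + m·FN + FP + c·TP)
- PPV = (1−c)TP / (TP + FP) = (1−c) × true PPV

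| c | m | Sensitivity | Specificity | PPV |
|---|---|---|---|---|
| 0 | 0 | 80% | 90% | 47% |
| 25% | 0 | 5.04/6.72 = 75% | 68.04/77.28 = 88% | 5.04/14.28 = 35% |
| 50% | 0 | 3.36/5.04 = 67% | 68.04/78.96 = 86% | 3.36/14.28 = 24% |
| 50% | 50% | 3.36/4.20 = 80% | 68.88/79.80 = 86% | 24% |
| 25% | 50% | 5.04/5.88 = 86% | 68.88/78.12 = 88% | 35% |

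**What the formulas show.** PPV falls by the factor (1−c), whatever m is. Sensitivity falls if c exceeds m, is unchanged if they are equal, and rises if m exceeds c. Specificity falls by a few points, unless nearly all cleared cases are MRI misses.

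**Other assumptions.** At 7% involvement (5.88 involved margins, TP = 4.70, FP = 7.81), c = 50% and m = 0 again give sensitivity 67%, while PPV goes from 38% to 19%. With specificity 84% in place of 90%, the same c and m take PPV from 36% to 18% at 10% involvement and from 27% to 14% at 7%.

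**The case against.** The strongest reply is that the decisive step is not in the text. No section says that the surgeon changes the retroperitoneal plane because of the MRI. Section 3.4 gives MRI for staging, section 3.2 ties surgery to one technique, and section 3.11 says only that nobody in the treating team is blinded. This stands: the mechanism is open under the protocol, but its frequency is unknown.

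A reader might infer that the bias runs only against correct positive calls, so that sensitivity, specificity and PPV must all be too low. The documents do not support that. Every patient also has a CT, the surgeon is unblinded without any exception for it, and operative findings can also lead to a wider plane. Misses cleared in this way raise apparent sensitivity.

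The involvement rate is also weak as an input. The 7-10% is a rate observed after surgery, so any clearing of margins would already have lowered it. About 8 involved margins also give little precision: the exact 95% interval for 6 of 8 is 35% to 97%, wide beside a shift of 5 to 13 points in sensitivity. This too stands. It limits what the illustration can show, but imprecision does not remove a systematic misclassification.

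Finally, the endpoint wording may be shorthand for infiltration of the retroperitoneal surface, with the definition left to an analysis plan that is not shown. That reading is possible, and it rules out saying that the endpoint cannot address the question in section 1.1. But a later plan could not recover an imaging-driven change of plane that nobody recorded.

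**Conclusion.** The point holds as a weakness in how one secondary endpoint is specified. As worded, the reference for retroperitoneal accuracy can be altered by the imaging it is meant to judge, and nothing in the protocol prevents, records or accounts for that. Where flagged margins are cleared, PPV is biased downward and specificity slightly so. Sensitivity is biased downward if only MRI-flagged cases are cleared; otherwise its direction is indeterminate.

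The size cannot be derived from the documents. The illustrative halving of PPV at c = 50% rests on assumed involvement, accuracy and clearance. It shows that moving about three patients (0.5 × 6.72 = 3.4) matters when only about 8 margins are involved. It does not predict the trial's result. The primary endpoint and N = 120 are not affected. This is a cheap improvement, not a flaw that threatens the study.

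**What to change.** - In section 3.8, define the reference for this endpoint as histological tumour invasion of the retroperitoneal surface or fascia, including any retroperitoneal tissue removed en bloc. This is close to the tumour feature that section 1.1 already describes.
- Record the MRI margin call before surgery.
- Add an item to the operative form stating whether the plane was changed because of imaging.
- Report final margin status separately as a surgical outcome. Give accuracy against the margin only as a secondary analysis for comparison with the literature, with and without the imaging-changed cases.

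The cost is protocol wording, one pathology form item, one operative form item and a dated MRI call. The same specimen serves. Comparison with earlier margin-based studies becomes slightly less direct, which the secondary analysis largely covers. No change to surgical care or blinding is proposed.

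### For nearby-organ infiltration the reference is specimen pathology and the surgeon is not blinded to MRI, so MRI misses may go unverified more often than MRI detections, and sensitivity and NPV may be biased upward

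*Protocol*

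**What the plan says.** Protocol 3.8 makes accuracy for spread to the peritoneum or an adjacent organ one joint secondary endpoint: "Diagnostic accuracy in peritoneal or nearby organ infiltration", assessed one month after surgery.

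The reference is pathology. Section 2.1 states: "Imaging findings will be compared with the histopathologic results of the specimen following surgical resection". Section 3.4 adds CT: "The evaluation of the diagnostic accuracy will be based on the cross-examination with the CT scan and the pathology results". Section 3.13 has the specimen's pathology recorded at the one-month reassessment. It also mentions standard monitoring with CT and MRI, but does not tie these to the endpoint. No operative finding, biopsy or follow-up result is named as the reference for tissue that stays in the patient.

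On order and blinding, patients "will be preoperatively submitted to MRI for staging" (3.4), and section 3.11 says: "There will be no blindness at the level of the patient, the treating physicians (surgeon, oncologist, radiotherapist". Section 3.2 ties the operation to "criteria surgical resection based on the principles of complete mesocolic excision (CME". The protocol sets no rule for an adjacent organ that was not removed.

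**The concern.** Pathology can show infiltration inside an organ only if the organ is in the specimen. Whether it is there is decided at an operation by a surgeon who is free to know the MRI result. If that result carries any weight, an organ that MRI calls infiltrated is more likely to be removed and examined than one that MRI calls clear. Verification then depends on the test being evaluated, even among patients who all have a specimen. This is separate from patients who are never resected and from the retroperitoneal margin, which is its own endpoint.

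At stake are sensitivity and NPV for organ infiltration. The introduction (1.1) presents more precise imaging-based staging as a route to selecting patients with advanced disease for neoadjuvant treatment. For that use, missed infiltration is the error that matters, and it is the error this reference can hide.

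**Working it through.** **Figures in the plan.** The protocol gives no accuracy figure for this endpoint. The sample size in 3.9 rests on T stage and does not bear on the point. It is used here only for scale: 120 patients less 30% dropout leaves 120 × 0.70 = 84.

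**Inputs, all assumed.** Let s be true sensitivity, f the fraction of MRI-missed infiltrated organs not removed, and g the fraction of MRI-detected infiltrated organs not removed. The documents give none of these.

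**Sensitivity.** Among infiltrated organs, verified detections are s(1−g) and verified misses are (1−s)(1−f). So

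apparent sensitivity = s(1−g) / [s(1−g) + (1−s)(1−f)].

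Prevalence cancels. Only the ratio (1−f)/(1−g) matters.

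| s | f | g | Calculation | Apparent sensitivity |
|---|---|---|---|---|
| 75% | 25% | 0 | 0.75/(0.75+0.1875) | 80% |
| 75% | 50% | 0 | 0.75/(0.75+0.125) | 86% |
| 75% | 50% | 25% | 0.5625/(0.5625+0.125) | 82% |
| 75% | 50% | 50% | 0.375/(0.375+0.125) | 75% (no bias) |
| 60% | 50% | 0 | 0.60/(0.60+0.20) | 75% |
| 60% | 50% | 25% | 0.45/(0.45+0.20) | 69% |

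The bias is upward when f exceeds g, nil when they are equal, and downward if g exceeds f.

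**Scale.** The 7–10% in 1.1 is for retroperitoneal margin infiltration in caecal and right-colon tumours. Borrowed as an assumed prevalence of organ infiltration, it gives 84 × 0.07 = 5.9 to 84 × 0.10 = 8.4 infiltrated cases. With 8.4 cases and s = 75%, MRI misses 8.4 × 0.25 = 2.1. Hiding half of them, about one patient, moves sensitivity from 75% to 86%.

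**NPV.** Assume 10% prevalence, 90% specificity, s = 75% and f = 50%, with unremoved organs read as clear. True negatives are 75.6 × 0.90 = 68.04 and misses are 2.1, so true NPV is 68.04/70.14 = 0.970. With 1.05 misses read as clear it becomes 69.09/70.14 = 0.985. NPV uses only MRI-negative patients, so g does not enter. NPV is raised whenever f is above zero, even if sensitivity is unbiased.

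**Effect of excluding unverified patients.** In the same example with g = 0, detections are 6.3, verified misses 1.05 and unverified misses 1.05.
- Unverified counted as not infiltrated: 6.3/(6.3+1.05) = 86%.
- Unverified excluded: 6.3/(6.3+1.05) = 86%, because neither detections nor counted misses change.
- Unverified counted as infiltrated: 6.3/(6.3+2.1) = 75%.
- If two further MRI-negative unverified patients are truly clear, counting all as infiltrated gives 6.3/(6.3+4.1) = 61%. This bound is therefore conservative.

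**The case against.** A reader might infer that the protocol scores an organ left in place as a true negative. It does not say so; no section gives a scoring rule. The inference is not needed for the direction on sensitivity, since leaving such patients out of the analysis removes the same misses. How unverified results are classified could also be settled in an SAP that is not shown. What an SAP cannot do is recover organ status if the data never separate organs removed and clear from organs not removed.

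A reader might also infer that sensitivity must be inflated, in the extreme up to 100%. That requires removal to follow MRI closely. Section 3.11 says only that the surgeon is not blinded; it does not say that MRI decides the extent of resection. The surgeon also has CT and may see adherence at operation. If removal follows those rather than MRI, f and g converge and the bias in sensitivity disappears. This objection stands, and it is why g belongs in the formula.

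Tumour at the specimen surface may also be reported, and under the joint wording of 3.8 it might already count as positive, so an absent organ need not mean absent evidence. That stands too. Finally, this is one component of one of three secondary endpoints; it does not touch the sizing of the primary endpoint.

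**Conclusion.** The concern holds conditionally. Specimen-only pathology and an unblinded surgeon allow verification of nearby organs to depend on MRI. If it does, so that f exceeds g, sensitivity is biased upward; NPV is biased upward whenever missed organs are left in place. For an assumed s of 75% and f of 50%, apparent sensitivity runs from 86% at g = 0 to 75% at g = 50%. These values are illustrations. The real size is unknown and may be small, and the protocol as written provides no way to learn it. The documents do not support saying that unremoved organs are counted as negative, or that inflation is certain.

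**What to change.** In 3.8, analyse nearby-organ infiltration separately from peritoneal infiltration. Record for each patient whether the adjacent organ was removed, and classify the organ reference as:
- infiltrated: tumour in the removed organ;
- not infiltrated: organ removed and clear, or tumour clear of the specimen surface facing that organ;
- unverified: tumour at that surface and organ not removed.

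Do not count unverified as negative. Report the number unverified by MRI result. Give sensitivity and NPV twice, with all unverified patients counted as not infiltrated and with all counted as infiltrated. If some unverified patients are MRI-positive, these two counts need not bracket sensitivity, so also show the two mixed assignments by MRI result. Do not present exclusion of unverified patients as a correction.

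The cost is endpoint wording and one extra data field. The protocol does not describe the content of the pathology report, so check that it states the status of the facing surface. The reported sensitivity will have a wider range and may be less favourable, and the worst-case bound is conservative. Surgery and other clinical management do not change.

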3.9 Calculation of the sample size

The sample size calculation was based on the primary endpoint. According to the literature, the specificity of MRI of the T1/T2 vs T3/T4 differentiation is 84%. Therefore, for a prospective study with alpha: 5%, power: 80%, d=10% and dropout rate: 30%, the estimated number of patients is 120.

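### The 80% power in section 3.9 is stated for a specificity, but neither the reference-negative T class nor its share of the 84 evaluable patients is given, and with T1/T2 as that class it is not reached at an assumed 20-40%

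*Protocol*

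**What the plan says.** Protocol section 3.7 defines the primary endpoint only in general terms: "Evaluation of diagnostic accuracy in the T stage assessment". It names neither an index nor a positive class.

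Section 3.9 says "The sample size calculation was based on the primary endpoint" and gives one planning rate: "According to the literature, the specificity of MRI of the T1/T2 vs T3/T4 differentiation is 84" (per cent). The remaining inputs and the result are "alpha: 5%, power: 80%, d=10% and dropout rate: 30%, the estimated number of patients is 120". The section does not state the formula, the null value, the sidedness, which T class counts as negative, the expected T-stage mix, or whether d is a difference to detect or a margin of error.

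Entry is not limited by T stage. Section 3.2 reads "The study will include patients with colon cancer that will meet the current criteria surgical resection", the disease criterion in section 3.3 is "Histologically confirmed colonic adenocarcinoma", and section 3.4 reads "All prospectively included patients with colon cancer will be preoperatively submitted to MRI for staging". Under section 2.1 the reference is the pathology of the resected specimen, so a patient's true T class is known only after surgery.

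**The concern.** A specificity has only the reference-negative patients in its denominator. With both T classes enrolled, that denominator is a fraction of the evaluable patients. Nothing in section 3.9 represents this fraction.

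If the calculation treated every evaluable patient as reference-negative, the 80% power overstates what the study can deliver on the quantity used to size its primary endpoint. The width of the confidence interval for specificity would be affected in the same way. A reader who relies on section 3.9 cannot tell whether either target is met.

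**Working it through.** **Inputs from section 3.9.** Specificity 0.84, alpha 0.05, power 0.80, d = 0.10, dropout 0.30, N = 120. Evaluable: 120 × 0.7 = 84. Normal quantiles: 1.96 (two-sided 5%), 1.645 (one-sided 5%), 0.8416 (80% power).

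**Input not in the documents.** The pT1/T2 share. I assume 20-40%, that is 17-34 of 84, which leaves 50-67 in T3/T4.

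**Step 1: reproduce 120 from the stated inputs alone.**
- One-sided, single variance: (1.645 + 0.8416)² × 0.84 × 0.16 / 0.10² = 83.09, rounded up to 84; 84/0.7 = 120 exactly.
- Two-sided, null 84% against 94%: (1.96·√(0.84×0.16) + 0.8416·√(0.94×0.06))² / 0.10² = 84.35; 84.35/0.7 = 120.5. Rounded up first, 85/0.7 = 121.4, so 122. This match is close, not exact.

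Neither formula has a term for the T mix, so both need about 84 reference-negative patients. Under either, any real mix of T classes gives less than 80%.

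**Step 2: readings that reach 120 with an unstated share.**
- Margin of error: 1.96² × 0.84 × 0.16 / 0.10² = 51.63; 51.63/0.615/0.7 = 120. This does not use the stated power.
- Null 94%, true value 84%, two-sided: (1.96·√(0.94×0.06) + 0.8416·√(0.84×0.16))² / 0.10² = 59.91; 59.91/0.713/0.7 = 120.

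The shares needed, about 61% and 71%, lie in the assumed T3/T4 range (60-80%) and outside the assumed T1/T2 range.

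**Step 3: reference-negative patients needed, out of 84 (normal approximation).**

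| Reading | Needed | Share of 84 |
|---|---|---|
| Null 94%, true 84%, one-sided | 49 | 58% |
| 95% half-width of 10 points | 52 | 62% |
| Null 94%, true 84%, two-sided | 60 | 71% |
| 84% against 94%, one-sided | 65 | 77% |
| One-sided, single variance | 84 | 100% |
| 84% against 94%, two-sided | 84.35 | all 84 give 79.8% |

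These break-evens are approximate. The exact binomial test for null 94% and true 84% first reaches 80% at 56 patients one-sided (67%) and 70 two-sided (83%).

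**Step 4: what 84 evaluable patients give.** With m reference-negative patients, power = Φ[(0.10·√m − z·√(p₀(1−p₀))) / √(p₁(1−p₁))], and half-width = 1.96·√(0.84×0.16/m). For example, 84% against 94%, two-sided, m = 34: (0.5831 − 0.7185)/0.2375 = −0.570, giving 28%.

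| | T1/T2 negative (17-34) | T3/T4 negative (50-67) |
|---|---|---|
| 84% against 94%, two-sided | 10-28% (exact: at most 40%) | 48-66% (exact: about 40-70%) |
| 84% against 94%, one-sided | 21-47% (exact: at most 49%) | 67-82% (exact: 59-82%) |
| One-sided, single variance | 30-48% | at most 72% |
| Null 94%, true 84%, one-sided | at most 70% (exact: at most 63%) | 80% reached from 49 (exact: first at 56) |
| 95% half-width, points | 17.4 to 12.3 | 10.2 to 8.8 |

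**Step 5: does dropout explain it?** With none of the 120 lost, 20-40% is 24-48 patients and the half-width is 14.7 to 10.4 points, still above 10.

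**The case against.** The strongest objection is that the formula is inferred. Section 3.9 states no T-stage share, so looking only at formulas that use its stated inputs excludes in advance every formula that allows for a split. Two readings with a share of about 61% or 71% also give 120, and on those the target is met under the normal approximation. Of the two formulas that need no share, only the one-sided version gives exactly 120 under ordinary rounding, and section 3.9 does not say that alpha is one-sided. The size of any shortfall also rests on a class assignment and a T mix that the documents do not supply.

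Most of this stands, and it limits the point. A reader might infer that 120 is an arithmetic error, that the authors certainly ignored the T mix, or that the trial is known to have 10-28% power. The documents support none of these: 84/0.7 = 120 is correct, the formula is not given, and that power range holds only with T1/T2 as the negative class, the assumed share, and a two-sided test of 84% against 94%.

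The objection does not rescue the stated power. The readings with a share need T3/T4 as the negative class unless T1/T2 is far more common than assumed. Section 1.1 aims to identify advanced disease for neoadjuvant treatment, which makes T3/T4 the natural target and T1/T2 the natural negative class. The margin-of-error reading leaves the 80% with no role. Nor can the matter be left to an analysis plan that is not shown, because the protocol itself states the power, its inputs and the resulting number.

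**Conclusion.** The point holds in this form: section 3.9 states 80% power for a specificity without the two inputs, negative class and share, on which that power depends.

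- **T1/T2 negative, assumed 20-40%:** none of the readings in the working reaches 80% power, and a 10-point half-width is not met.
- **T3/T4 negative:** the 10-point half-width is about met. Power is 48-66% for a two-sided test of 84% against 94%, while some other tests reach 80%.

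Confidence is medium, because the formula, the negative class and the T mix are all unstated. It should be fixed, since the 80% is the stated basis for the size of the primary endpoint and a reader cannot confirm it. The calculation does not by itself show that more patients are needed.

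**What to change.** Keep 120 patients and rewrite the paragraph in section 3.9 so that it:

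1. names the positive class and the assumed T-stage share;
2. says whether d is a margin of error or a difference to detect;
3. gives the expected specificity and sensitivity denominators among the 84 evaluable, with 95% half-widths. For example, at 30% pT1/T2 with T3/T4 positive, these are 25 and 59 patients, and 1.96·√(0.84×0.16/25) = 14.4 and 1.96·√(0.84×0.16/59) = 9.4 points if each rate is 84%;
4. removes the 80% power, or replaces it with the power achieved for a stated null, alternative and sidedness.

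The cost is one reworded paragraph, with no added patients and no change to conduct. The downside is that the stated power, and possibly the stated precision, will look less favourable.
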